## 7. STUDY CALENDAR & EVALUATIONS

Study Evaluation Cycle = 21 days	Screening 	Cycle 1	Cycle 2+	Safety follow up visit 	Long-term Follow up 
	-28 days from C1D1	Day 1 ± 3 days	Day 1 ± 3 days	30/90 days post last dose + 7 days	Every 6 months (±14 days)
REQUIRED ASSESSMENTS					
Informed Consent	X				
Medical History and Disease Staging 	X				
Physical Exam	X	X	X	D30	
Vital signs and ECOG Performance Status 	X	X 	X 	D30	
ECG 	X	X 	X 		
AEs & concomitant medications	X	X	X	X	
LABORATORY ASSESSMENTS					
Complete Blood Cell Count with diff (CBC) 	X	X 	X	D30	
Comprehensive Metabolic Profile (CMP) 	X	X 	X 	D30	
PT/INR and aPTT 	X				
Thyroid Function Testing 	X		X 		
Urine protein 	X		X 		
Chromogranin A, neuron specific enolase and urine NTx 	X		X 	D30	
Prostate-specific antigen (PSA) 	X		X	D30	X 
Testosterone 	X			D30	
DISEASE ASSESSMENT					
CT of chest 	X		X 	D30 	X 
CT or MRI of abdomen and pelvis 	X		X 	D30 	X 
MRI Brain 	X		X 	D30 	X 
Bone scan 	X		X 	D30 	X 
TREATMENT EXPOSURE					
Lenvatinib		D1-21	D1-21		
Pembrolizumab		X	X		
SPECIMEN COLLECTION					
Archival Tumor Tissue 	X 				
Blood for somatic baseline		X			
Blood for plasma 		X 		D30 	
Stool for microbiome 		X 			
FOLLOW-UP					
Survival Status, Subsequent Therapy					X

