4: Chromogranin A, neuron specific enolase and urine NTx (optional) will be performed at screening/day 1 then prior to treatment every other Cycle starting at Cycle 3 Day 1 then at the D30 safety visit. PSA should be obtained at screening then prior to treatment every Cycle then at the D30 safety visit. Subjects that come off study without progression should have PSA obtained per investigator discretion. Testosterone will be performed at screening and at the D30 safety visit.

5: Tumor response assessment will consist of evaluation by CT scans of chest and MRI or CT of abdomen and pelvis. If a PET/CT is done for tumor assessment and if tumor/s are visible on the CT, this may be used for tumor evaluation. A bone scan will be obtained at screening and with other radiology imaging at the frequency as outlined below. An MRI of the brain should be performed at screening if there is a concern for the presence of brain metastases. Tumor imaging will be done at screening and every 3 cycles (9 weeks) for the first 12 cycles (36 weeks) and then every 4 cycles (12 weeks) until the patient is off study therapy (window of  $\pm$  1 week). Tumor imaging should follow week intervals in the case of study treatment delays due to toxicities. During follow up after completion of study treatment, imaging frequency is at the discretion of the site investigator. Imaging selected for each subject should remain the same throughout the study. Tumor imaging to be done at treatment discontinuation/safety follow up visit is at discretion of site investigator. If tumor assessments are available for subjects who have not yet experienced progressive disease (PD) at the time treatment is discontinued, the follow-up tumor evaluations will be documented in the eCRF until PD or death is confirmed, or until another treatment is initiated.

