## 9.7 Evaluation of Best Overall Response

Target Lesions	Non-Target Lesions	New Lesions	Overall Response
CR	CR	No	CR
CR	Non-CR/ Non-PD	No	PR
CR	Not evaluated	No	PR
PR	Non-PD/ or not all evaluated	No	PR
SD	Non-PD or not all evaluated	No	SD
Not all evaluated	Non-PD	No	Non-evaluable
PD	Any	Yes or No	PD
Any	PD*	Yes or No	PD
Any	Any	Yes	PD

\*In exceptional circumstances, unequivocal progression in non-target lesions may be accepted as disease progression.

Subjects with a global deterioration of health status requiring discontinuation of treatment without objective evidence of disease progression at that time should be classified as having “symptomatic deterioration.” Every effort should be made to document the objective progression even after discontinuation of treatment.

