### 9.8.2 Radiologic Progression Free Survival (rPFS)

rPFS has two components to its definition. For soft tissue lesions, rPFS will be measured from Cycle 1 Day 1 to date of radiologic progression per RECIST 1.1 or death from any cause, whichever occurs first. For bone lesions (non-measurable disease), rPFS will be measured from Cycle 1 Day 1 to date of progression per PCWG3 criteria [9] or death from any cause, whichever occurs first. Thus, the “date of progression” is the earlier date of either of those two possible types of progression. Subjects who have not progressed will be right-censored at the date of the last disease evaluation.

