### 12.3 Study Design and Interim Analyses

An open label phase II study design of lenvatinib and pembrolizumab in metastatic NEPC is planned with primary endpoint of 6-month radiologic progression-free survival (rPFS), yes/no. For this binary endpoint, a 2-stage Simon near optimal design will be used, with these input parameters:  $p_0 = 0.10$ ;  $p_1 = 0.25$ ;  $\alpha = 0.125$ ; and power = 0.90. This results in the following design features:  $N_1 = 27$ ;  $R_1 = 2$ ;  $N = 40$ ;  $R = 6$ ;  $PET = 0.485$ ; and  $ASN = 33.70$ .

Hence, if there are at least 3 successes (patients who have had  $\geq 6.00$  months of rPFS) in the 27 patients in Stage 1 then the study will proceed to Stage 2, otherwise it will terminate early. If there are at least 7 successes in the final total of 40 patients, then the treatment will be considered promising. To allow for up to 20% of registered patients becoming non evaluable, up to 50 patients will need to be enrolled to yield 40 evaluable patients.

It may become necessary to temporarily suspend accrual at or near the completion of Stage 1 of the study in order to evaluate the 6-month rPFS (primary endpoint) of the last few Stage 1 patients. If Stage 1 accrual is at say, 24 patients and there have been no successes (i.e., no patients who have had  $\geq 6.00$  months of rPFS), then Stage 2 of accrual could not begin until up to 3 more patients are enrolled in Stage 1 and their rPFS outcome (success or not) has been determined.

Conversely, if  $\geq 3$  successes have been observed within the first 24 or fewer patients, then the interim analysis can be omitted, and accrual could continue into Stage 2 without interruption. There would be no need for a temporary suspension of accrual.

The study design operational characteristics were calculated using the “Two Stage Phase II Clinical Trials” program in the PASS (2019) software [10]. PET is the probability of early termination under the null hypothesis that  $p = 0.10$ . ASN is the average sample number, which is what is minimized in a Simon optimal (or near optimal) design. ASN is the mean number of patients required to complete a given Simon optimal (or near optimal) design after many hypothetical replications of the trial, wherein some trials terminated early (i.e., after Stage 1, with only  $N_1$  patients) and the others did not (i.e., went on to Stage 2, using a total of  $N$  patients).

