## 12.4 Analysis

### 12.4.1 Primary Objective

For the Primary objective (efficacy assessment), the binary endpoint (rPFS  $\geq$  6.00 months, yes/no) will be summarized with its point estimate (an occurrence rate), and 2-sided Wilson type 95% confidence interval (CI).

The duration of censored rPFS will be estimated with standard Kaplan-Meier (K-M) methodology. Point and CI estimates of the median and various timepoint-specific rPFS rates will be derived from the K-M life table (e.g., 6 month rate, 12 month rate, etc.), each with its own respective CI. A graph of the K-M curve for rPFS will be generated along with the Hall-Wellner 95% confidence band, and a display of the number of patients at risk at several time points, below the X-axis.

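### The 9-week scan grid lets progression first seen at week 27 count as a 6-month success, so the reported 6-month rPFS rate overstates the proportion progression-free at 6 months

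*Combined protocol and SAP*

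**What the plan says.** - **Endpoint.** Section 12.3 describes the design "with primary endpoint of 6-month radiologic progression-free survival (rPFS), yes/no". Success there and in 12.4.1 is rPFS of at least 6.00 months. Sections 9.8.2 and 12.2.1 run rPFS from Cycle 1 Day 1 to the date of progression or death. A month is not defined in days.
- **Scans.** Section 7, footnote 5: "Tumor imaging will be done at screening and every 3 cycles (9 weeks) for the first 12 cycles (36 weeks", with a window of one week either side. It adds: "Tumor imaging should follow week intervals in the case of study treatment delays due to toxicities". The start of the 9-week count is not named. The calendar allows screening up to "28 days from C1D1".
- **Analysis.** Section 12.4.1 reports the binary rate with a Wilson interval and says "various timepoint-specific rPFS rates will be derived from the K-M life table (e.g., 6 month rate, 12 month rate, etc".
- **Censoring.** Section 9.8.2: "Subjects who have not progressed will be right-censored at the date of the last disease evaluation". Nothing says how a patient censored before 6.00 months enters the yes/no count. Section 12.6 keeps such a patient evaluable after one cycle and imaging.
- **Reference rate.** Section 1.5 refers to historical controls or contemporary phase II studies. It gives no source, scan interval or timing rule for the 10%.
- **Duration.** Section 12.7 allows 6 months after accrual to obtain the primary endpoint.

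**The concern.** Radiographic progression can be dated only when a scan shows it. The nominal scan days around the landmark are 126 and 189, and 6.00 months lies between them. A patient whose disease progresses in month 5, and who is neither scanned early nor dies before 6.00 months, is found on the week-27 scan, gets an rPFS of about 6.2 months, and counts as a success.

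Week 18 is therefore in practice the last scheduled scan that can produce a radiographic failure. The quantity called a 6-month rate lies closer to the proportion with no progression at about 4.1 months who are also alive, with no progression on an unscheduled scan, at 6.00 months. Readers who set the result against 10% and 25% would take it as something more favourable than it is.

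**Working it through.** **1. The plan's own design (12.3).** Exact two-stage binomial: P(promising | p) = sum over x = 3 to 27 of Bin(x; 27, p) × P(Bin(13, p) ≥ 7 − x).
- p = 0.10: PET = P(X ≤ 2 of 27) = 0.485; ASN = 27 + (1 − 0.485) × 13 = 33.70; alpha = 0.098.
- p = 0.25: power = 0.900.

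These agree with the stated figures and respect the 0.125 limit.

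**2. Scan days.** Cycles are 21 days (section 5), so scans from Cycle 1 Day 1 fall on days 63, 126 and 189. Taking 30.4375 days per month (assumption), 6.00 months = 182.625 days.
- Day 126 / 30.4375 = 4.14 months.
- Day 189 / 30.4375 = 6.21 months.
- Week-27 window, days 182 to 196: 5.98 to 6.44 months. Only day 182 falls short, so 14 of 15 days score as success.
- With a 30-day month, 6.00 months = 180 days and all 15 days score as success.

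**3. Size of the overstatement (illustrative).** Assume exponential rPFS with a true 6.00-month rate of 10%. Then S(126) = 0.10^(126/182.625) = 0.204, so 0.204 − 0.10 = 0.104 of patients have their event between the two dates. Let d be the share of these events that are deaths (0 or 30%) and c the share of the progressions caught early (both assumptions). The scored rate is 0.10 + 0.104 × (1 − d) × (1 − c).

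| c | d | scored rate | P(promising) |
|---|---|---|---|
| 50% | 0 | 0.152 | 0.40 |
| 50% | 30% | 0.136 | 0.30 |
| 75% | 0 | 0.126 | 0.23 |
| 75% | 30% | 0.118 | 0.18 |
| none | 0 | 0.204 | 0.73 |

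For the last case, simulating scan dates uniformly within one week either side gives a scored rate of 0.20 and P = 0.71. With 30% deaths these are 0.17 and 0.52.

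The P(promising) column is a type I error only if the 10% reference is itself a true 6-month rate. If the reference was scored by scan date with the same gap, the scored null rate is 10% and the error is 0.098.

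**4. What a week-27 landmark would do at 7/40.** Progression first seen on that scan counts as failure (nominal day 189).
- p0 and p1 true 6.00-month rates: 0.10^(189/182.625) = 0.092 and 0.25^(189/182.625) = 0.238; alpha 0.070, power 0.868.
- p0 and p1 scored with the same gap, no deaths: the reference rate is S(126), so S(189) = p^(189/126), giving 0.032 and 0.125; power 0.22.
- Same gap, 30% deaths: 0.043 and 0.154; power 0.41.

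**5. Follow-up.** A patient clean at week 18 and not yet rescanned is censored at day 126 under 9.8.2. Success is settled by the week-27 scan, as late as day 196. That is 196 − 182.625 = 13.4 days beyond 6.00 months.

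**The case against.** The plan's rule can be applied as written. Dating progression by the scan that shows it is the stated definition, and given the scan dates every progression has a score. Section 12.3 is internally consistent and correctly calculated. This stands, and it is why the decision count should be kept.

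Detection before week 27 is also likely. Physical examination and PSA are scheduled every cycle, scans may be done sooner for clinical reasons, and section 9.7 asks: "Every effort should be made to document the objective progression even after discontinuation of treatment". Deaths before 6.00 months always fail, including deaths after unseen progression, which the calculation does not remove. So 0.52 to 0.71 is an upper bound, and the 50% to 75% range is an assumption without a source in the plan.

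A reader might go further in three ways that the documents do not support:
- **That the type I error is inflated.** This needs the 10% to be a true 6-month rate. Section 1.5 does not say whether it is.
- **That the scan anchor is open.** Screening may precede Cycle 1 Day 1 by 28 days. But the interval is counted in cycles and 12 cycles are equated with 36 weeks, so Cycle 1 Day 1 is the natural reading. It is only unwritten.
- **That early-censored patients could be scored either way.** Section 12.3 counts patients who have had 6.00 months of rPFS. A patient censored earlier has not shown that, so non-success is the natural reading, though no sentence says it.

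**Conclusion.** The reporting point holds however p0 was timed: with scans counted from Cycle 1 Day 1, both 6-month estimates in 12.4.1 credit some patients who had already progressed by 6 months. Under the exponential illustration a true 10% would be reported as about 12% to 15%, and at most 17% to 20%. These sizes depend on the assumed event distribution, share of deaths and early detection. The 14-of-15 count depends on the month length.

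An inflated go/no-go error is conditional and not established. It is 0.098 if the reference shares the scan gap. If the reference is a true 6-month rate, it is 0.18 to 0.40 with 50% to 75% caught early, and at most 0.52 to 0.71. Nor do the documents support replacing the decision endpoint by default, since the landmark's power at 7/40 runs from 0.87 down to 0.22 depending on the same unstated fact. This is an inexpensive improvement to reporting and wording.

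**What to change.** 1. **Section 12.4.1.** Keep the scan-date count for the 3/27 and 7/40 decision. Beside it, report the proportion alive and progression-free on the week-27 scan (one week either side) or a later one, with a Wilson interval. Progression first seen on that scan counts as failure, and a clean scan on day 182 is accepted. Off-treatment imaging is discretionary, so also give the number with no such scan.
2. **Kaplan-Meier.** Report the rate just after day 196 as well as at 6.00 months.
3. **Section 12.7.** Allow endpoint follow-up through day 196. Section 12.3 already has Stage 2 wait, where needed, until "their rPFS outcome (success or not) has been determined", so the Stage 1 rule need not change.
4. **Before the Stage 1 count,** state the source of p0 and p1 and how progression was timed in it. Only if they are true 6-month rates consider making the landmark the decision endpoint (alpha 0.070, power 0.868).
5. **In the same edit,** write down that scan weeks count from Cycle 1 Day 1, what 6.00 months is in days, and that evaluable patients censored before 6.00 months are non-successes.

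Cost: no added scans, about two weeks' longer endpoint follow-up, and a supporting rate that will look less favourable than the scan-date count. The landmark also sits slightly past 6 months, so it reads a little low (9.2% for a true 10%, 23.8% for a true 25%).

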#### **6.7 Long Term Follow Up**

For subjects who discontinue for reasons other than progressive disease, radiographic disease assessment should be performed per discretion of the site investigator per standard of care for disease assessment. The scan interval may be reset if scans were done sooner for clinical reasons and the type of scan may be left to discretion of the site investigator. This imaging may be done locally. Follow up for these subjects will occur every 6 months until progression. Once disease progression is documented, subjects will be followed for survival every 6 months for 5 years from the time of documented progression. Follow up may be accomplished via clinic visit, phone

call, or other avenues as appropriate. A window of  $\pm$  14 days will be applied to long term follow up.

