## 12.2 Endpoints

### 12.2.1 Definition of Primary Endpoint

rPFS is defined as the date of Cycle 1 Day 1 to date of radiologic progression of soft tissue lesions per RECIST 1.1 or death whichever occurs first. rPFS is defined as the date of Cycle 1 Day 1 to date of progression of bone lesions (non-measurable disease) per PCWG3 criteria or death whichever occurs first. Censoring of rPFS is described in Section 9.8.2.

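### A death after month 6 scores as a 6-month rPFS success even when no scan was done near month 6

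*Combined protocol and SAP*

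**What the plan says.** Section 9.8.2 defines the endpoint for soft tissue: "rPFS will be measured from Cycle 1 Day 1 to date of radiologic progression per RECIST 1.1 or death from any cause, whichever occurs first". The matching rule for bone runs "to date of progression per PCWG3 criteria [9] or death from any cause, whichever occurs first". Its only censoring rule is "Subjects who have not progressed will be right-censored at the date of the last disease evaluation". Section 12.2.1 adds nothing further: "Censoring of rPFS is described in Section 9.8.2".

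Section 12.3 turns this into a yes/no outcome. A success is a patient with at least 6.00 months of rPFS, and Stage 2 needs 3 successes in 27. "If there are at least 7 successes in the final total of 40 patients, then the treatment will be considered promising". No progression-free scan near month 6 is required.

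On treatment, footnote 5 of the study calendar fixes scans every 9 weeks for the first 36 weeks, with a window of 1 week either side. Once treatment stops without progression, the same footnote and section 6.7 leave imaging to the site investigator. Section 6.7 says "Follow up for these subjects will occur every 6 months until progression", and this follow-up may be by phone. Footnote 5 says of any available scans that "the follow-up tumor evaluations will be documented in the eCRF until PD or death is confirmed, or until another treatment is initiated". Survival status continues to be collected. Under section 12.6, one cycle of treatment plus disease imaging makes a patient evaluable for efficacy.

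**The concern.** Take a patient who stops treatment without documented progression and is not scanned again. If he dies after month 6, the death is his rPFS event at its own date, so his rPFS equals his overall survival and he is a success. If he is alive at the data cut, he is censored at the old scan, short of 6 months. Whether his unscanned months count as progression-free thus depends on whether he later dies.

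This goes further than an unstated convention. For the deaths, the written rule gives a definite score, and that score credits progression-free time that nobody observed. These scores enter the 3/27 and 7/40 rules directly. The Kaplan-Meier estimates of rPFS in section 12.4.1 are affected in the same way.

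**Working it through.** **1. The plan's own figures.** Inputs from section 12.3: n1 = 27, r1 = 2, n = 40, r = 6, p0 = 0.10, p1 = 0.25.
- PET = P(X1 ≤ 2 | 27, 0.10) = 0.4846 (stated 0.485).
- ASN = 27 + (1 − 0.4846) × 13 = 33.70 (stated 33.70).
- P(promising) = Σ over x1 ≥ 3 of P(X1 = x1) × P(X2 ≥ 7 − x1 | 13, p). This gives 0.098 at 0.10 (limit 0.125) and 0.900 at 0.25 (stated 0.90).

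**2. The score.** Week 9 is 63 / 30.4375 = 2.07 months. With death at month 8, rPFS = 8.0 ≥ 6.00, a success. Alive, the patient is censored at 2.07.

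**3. Leverage of one patient.** 6/40 = 15.0% (Wilson 95% CI 7.1 to 29.1) is not promising. 7/40 = 17.5% (8.7 to 31.9) is.

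**4. Share of the unscanned group who die after month 6 but before the analysis.** Section 12.7 gives 16 to 30 patients per year and 6 months of follow-up after the last enrolment. Assumptions not in the documents: uniform accrual over A months, exponential survival with median 8 or 15 months, and a Stage 1 look 6 months after patient 27. With λ = ln 2 / median,

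s = e^(−6λ) × [1 − (1 − e^(−λA)) / (λA)].

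| Look | A (months) | s, median 15 | s, median 8 |
|---|---|---|---|
| Stage 1, 27 patients | 27/30 × 12 = 10.8 | 0.161 | 0.208 |
| Stage 1, 27 patients | 27/16 × 12 = 20.25 | 0.266 | 0.314 |
| Final, 50 patients | 50/30 × 12 = 20.0 | 0.263 | 0.312 |
| Final, 50 patients | 50/16 × 12 = 37.5 | 0.398 | 0.419 |

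So s is about 16 to 31% at Stage 1 and 26 to 42% at the final look. Section 12.7's printed accrual of 24 to 38 months gives 0.30 to 0.42 at the final look, inside that range.

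**5. Effect on the design.** Let q be the assumed share of patients who stop without progression before month 6 and are never rescanned. The scored rate under the null is 0.10 + 0.90 × q × s. PET uses the Stage 1 values of s, and P(promising) the final ones.
- q = 5%, PET: scored rates 0.1073 to 0.1141 give 0.44 to 0.39.
- q = 5%, P(promising): scored rates 0.1118 to 0.1188 give 0.15 to 0.19.
- q = 10%, PET: scored rates 0.1145 to 0.1283 give 0.39 to 0.31.
- q = 10%, P(promising): scored rates 0.1237 to 0.1377 give 0.22 to 0.30.

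**6. The offset.** If unscanned patients who are not dead by the look count as failures, the scored rate becomes 0.10 × (1 − q) + q × s. At the final look, q = 5% gives 0.0950 + 0.05 × (0.263 to 0.419) = 0.108 to 0.116, and P(promising) is 0.13 to 0.17. At q = 10% the scored rate is 0.116 to 0.132 and P(promising) is 0.17 to 0.27.

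**The case against.** Counting death from any cause at its own date is a usual PFS definition, and censoring such deaths brings informative censoring of its own. That stands for the Kaplan-Meier curve: the lack of a sensitivity analysis there is a gap, not an error. It does not rescue the yes/no endpoint, where the convention turns an unobserved interval into a positive result.

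The documents also push against long gaps. Section 9.7 asks sites to make every effort to document progression after treatment ends, and section 6.7 expects imaging per standard of care. Both should lower q, but neither sets a scan schedule or a scoring rule.

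Three stronger readings are tempting and are not supported.
- **Large inflation.** If 20% of patients were never rescanned and 45% of those died after month 6, the scored rate would be 0.10 + 0.90 × 0.20 × 0.45 = 0.181 and P(promising) 0.597. The documents give no basis for 20%. The 45% needs every patient followed to 24 months, whereas section 12.7 plans 6 months beyond the last enrolment.
- **Bias always toward a promising result.** This holds for the deaths alone. The unscanned group also contains true non-progressors who are alive and censored early. The plan does not say how they enter the yes/no count, and counting them as failures offsets part of the effect.
- **A contradiction between footnote 5 and section 6.7.** One limits how long available scans are entered in the eCRF, and the other how long patients are followed. They can coexist, so aligning them is tidying.

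**Conclusion.** The point holds. Sections 9.8.2 and 12.3, read together, score an unscanned patient who dies after month 6 as a success, and nothing elsewhere in the plan prevents it. Discretionary imaging after treatment makes the case possible, and one such patient can decide the trial at the 6/40 to 7/40 boundary.

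The size is conditional. With an assumed q of 5%, the chance of a false promising result is about 0.15 to 0.19 instead of 0.098, and PET is about 0.39 to 0.44 instead of 0.485. With q of 10%, the chance is about 0.22 to 0.30. These ranges rest on exponential survival, uniform accrual at section 12.7's rates, and no true success being lost through early censoring. They illustrate sensitivity and do not estimate what will happen.

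**What to change.** - **Sections 12.3 and 12.4.1.** Define success as no progression or death before 6.00 months, plus a progression-free disease evaluation at or after the scheduled week-27 assessment including its window, that is, from week 26 onward. Tie the rule to the window and not to 6.00 months: week 26 is 182 / 30.4375 = 5.98 months, so a compliant scan could otherwise fail.
- **Same sections.** State that efficacy-evaluable patients without such an evaluation are non-successes, whether they later die or are alive and censored early.
- **Section 9.8.2.** Add a Kaplan-Meier sensitivity analysis that censors at the last evaluation when death follows new anticancer therapy or two or more missed scheduled scans. Say that missed scans are counted against the on-treatment imaging calendar, since no interval is fixed afterwards.
- **Optional.** Give footnote 5 and section 6.7 the same end point for tumor documentation.

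Settle this before the Stage 1 decision, so that the rule is not chosen knowing who died. The cost is wording and one extra analysis, with no new visits or patients. The success count can only stay the same or fall, and some true non-progressors without a scan will count as failures. If these were 2.5% of patients, power at a true 25% rate would be the value at 0.25 − 0.025 = 0.225, which is 0.822 instead of 0.900.
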